#### **4.1.2.5 Defining the recommended Phase 2 dose for monotherapy**

The RP2D-M will be defined when all participants in Part A have completed a minimum of 28 days of treatment (ie, 1 Cycle) or have discontinued prematurely ([Table 1-4](#)). All safety, PK, available PD biomarker, ADA, and antitumor activity data will be used to select the RP2D-M.

The RP2D-M will not exceed the MTD (if an MTD is established). Pharmacodynamic effects consistent with the mechanism of action of UCB6114 and/or clinical evidence of antitumor activity may also help determine the RP2D-M.

#### **4.1.3 Part A1 – Dose optimization (alternative dosing schedules)**

Part A1 is a multicenter, non-randomized, open-label, dose optimization module of Study ONC001 to evaluate alternative dosing schedules and infusion times for UCB6114 administered as monotherapy in patients with unresectable locally advanced or metastatic colorectal cancer, gastric cancer, cancer of the gastro-esophageal junction, or pancreatic cancer.

Part A1 may commence after the fifth cohort in Part A (Cohort 5) is considered sufficiently █ by the SMC (DLT rate less than 33%). The planned dose optimization scheme for Part A1 will assess the safety and tolerability of the drug new formulation and will explore shortening of the infusion time and less frequent dosing as follows:

- Cohort 1: 2000mg Q2W (60-minute iv infusion), 28-day treatment cycle
- Cohort 2: 2000mg Q2W (30-minute iv infusion), 28-day treatment cycle
- Cohort 3: 3000mg Q3W (90-minute iv infusion), 21-day treatment cycle
- Cohort 4: 4000mg Q4W (120-minute iv infusion), 28-day treatment cycle

Details of each planned cohort are provided in [Table 6-6](#).

Up to 32 participants will be allocated 1:1:1:1 to one of the 4 cohorts, with each cohort enrolling 8 study participants including 1 sentinel participant with an observation period of 48 hours.

The enrollment of a sentinel participant in each cohort has been included as an additional risk mitigation measure to monitor infusion related reactions and other early onset treatment-related AEs. Each sentinel participant will be assessed for at least 48 hours following the first administration of UCB6114 in the first cycle and the SMC will convene before further participants within the cohort can be enrolled.

The SMC will also convene after 25%, 50% and 100% of study participants in Part A1 have completed the required 28-day observation period. If deemed necessary, an additional SMC meeting can convene after 75% of the participants have completed the required observation period. If 1 DLT, or more, (refer to Section 4.1.2.4 for the definition of DLTs) are reported for a cohort then, an ad-hoc SMC will convene to determine if the dosing schedule and study can continue as planned.

If 3 or more participants experience DLT(s) in a given cohort, no further participants will be enrolled in the cohort and the dosing schedule will be considered to be unacceptably toxic.

After consultation, the SMC will provide recommendations which could include to expand enrollment in a particular cohort to gain additional safety data, continue this Part with modifications or temporary suspension of enrollment in a particular cohort. Details are described in a SMC Charter.

The planned duration of treatment is 2 cycles. Participants may, however, remain in the study for additional cycles if they are receiving therapeutic benefit (SD, PR, or CR) or until they fulfill one of the criteria for treatment discontinuation. Participants will continue treatment until disease progression, unmanageable toxicity, or withdrawal from the study. Upon discontinuation from treatment, participant will be referred to appropriate follow-up care per the Investigator's judgment.

#### **4.1.4        Part B – Dose escalation with TFD/TPI**

Part B is a single arm open-label multiple ascending dose-escalation module of ONC001 evaluating UCB6114 in combination with TFD/TPI to identify the recommended Phase 2 dose of UCB6114 when used in combination with TFD/TPI (RP2D-T). Up to 27 participants with unresectable locally advanced or metastatic colorectal adenocarcinoma, gastric adenocarcinoma, or adenocarcinoma of the gastroesophageal junction will be enrolled.

Part B of ONC001 is planned to be initiated after Cohort 3 of Part A has completed the 28-day DLT assessment period and once the SMC has provided a recommendation to dose escalate to the next protocol-defined level in Part A of the study.

During the Treatment Period, UCB6114 will be administered in combination with TFD/TPI. UCB6114 will be administered as an iv infusion every 2 weeks (Q2W), while TFD/TPI will be administered orally twice daily (bid) within 1 hour of completion of morning and evening meals at home on Days 1 to 5 and Days 8 to 12 (28-day cycle). For the convenience of the participants, TFD/TPI can be administered at home to allow for the 12-hour interval between TFD/TPI doses associated with meals. For administration at home on Cycle 1 Day 1, eligibility must be confirmed within 3 days prior to Day 1 dosing as per the Schedule of Assessments.

Trifluridine/tipiracil will be administered at the recommended standard of care dose. The starting dose of UCB6114 in Part B will depend on the dose level evaluated in Cohort 3 of Part A (anticipated to be 500mg Q2W iv) and the emerging safety profile of UCB6114 monotherapy, including any overlapping toxicity with TFD/TPI.

Part B will be undertaken using the mTPI method. A target DLT rate of 25% with an equivalence interval (20% to 30%) will be used to estimate the MTD during dose escalation. For all dose levels, enrolled participants will be treated in cohorts of 2 to 4 participants (target of 3), who can

---

be treated in parallel. Each dose level may have more than one cohort and will have a minimum of 3 evaluable participants.

It is expected that up to 3 dose levels of UCB6114 will be explored in combination with the standard TFD/TPI dosing regimen. However, additional dose levels may be added based on emerging data and recommendations of the SMC. Dose escalation steps are currently planned at a maximum of 2-fold. Escalating dose levels in Part B will not exceed a dose level tested and considered safe by the SMC to allow dose escalation in monotherapy (Part A).

The decision to dose escalate, have no change in dose, or dose de-escalate in the next cohort will occur once all participants in the preceding cohort have been monitored for a minimum of 28 days (ie, 1 cycle). All available safety data (both within the cohort and from preceding cohorts and other parts of the study) will be taken into consideration when dose escalation decisions are made. The dose justification is given below in Section 4.3.3.

The planned duration of treatment is 2 cycles. Participants may, however, remain in the study for additional cycles if they are receiving therapeutic benefit (SD, PR, or CR) or until they fulfill one of the criteria for study discontinuation (Section 7.2). Participants will continue treatment until disease progression, unmanageable toxicity, or withdrawal of consent. Upon discontinuation of treatment, participants will be referred to appropriate follow-up care per the investigator's judgment.

From Part B, a RP2D-T for UCB6114 in combination with TFD/TPI will be determined based upon the totality of information, including the safety profile, PK data, PD biomarker data, and available antitumor activity.

#### **4.1.4.1 Study oversight**

The SMC will convene after the last participant in a given cohort has completed the required 28-day DLT Observation Period. The SMC will decide whether to halt dose escalation, further expand the dose level to gain additional safety data, or determine the next dose level to be tested.

Safety conference calls with investigators and key Sponsor personnel will be held regularly.

#### **4.1.4.2 Dose-limiting toxicity and maximum tolerated dose definition and determination**

##### **4.1.4.2.1 Definition of DLT**

Dose-limiting toxicity is defined as one of the following toxicities (according to the NCI CTCAE Version 5.0) occurring during the DLT assessment window (Days 1 to 28 of Cycle 1) that is at least possibly related to UCB6114:

- Grade  $\geq 4$  neutropenia (ANC  $<500/\mu\text{L}$ ) lasting  $\geq 7$  days
  - In the event of CTCAE Grade 4 neutropenia, full blood count must be performed on the seventh day after the onset of the event to determine if a DLT has occurred
- Grade  $\geq 3$  neutropenia complicated by fever ( $\geq 38^\circ \text{C}$ ) or infection
- Grade 3 thrombocytopenia with bleeding or requiring platelet transfusion or Grade 4 thrombocytopenia
- Any Grade  $\geq 3$  non-hematological event with the following exceptions:

---

- Grade 3 nausea, vomiting, diarrhea, or fatigue that resolves to Grade  $\leq 2$  within 24 hours of implementing optimal supportive care
- Grade 3 laboratory abnormality that is asymptomatic and also deemed by the investigator to not be clinically significant

Investigators, in consultation with the medical monitor, can declare a DLT if a participant is experiencing toxicity and treatment cannot be continued without exposing the participant to excessive risk.

#### **4.1.4.2.2 Determination of maximum-tolerated dose**

For every dose levels, participants will be treated in cohorts of 2 to 4 (target of 3), each dose level will have a minimum of 3 and a maximum of 9 participants.

The target rate of DLTs is 25% (equivalence interval 20% to 30%). The target rate will define the MTD of the combination regimen (UCB6114 given in combination with TFD/TPI).

The mTPI method relies upon a statistical probability algorithm, calculated using data from all participants treated in prior and current cohorts at the same dose level, to determine whether future cohorts should be dose escalated, have no change in dose, or be dose de-escalated. The dose escalation will stop if any of the following criteria is met:

- The maximum sample size has been reached (27 participants total)
- At least 9 participants have been accumulated on a dose that is predicted to be the MTD
- All doses explored appear to be overly toxic and the MTD cannot be determined
- The escalation would exceed a dose level tested and considered safe by the SMC in monotherapy (Part A)

The mTPI design uses a Bayesian decision framework to inform dose-escalation and dose de-escalation decisions. These rules are conceptually similar to those used by the 3+3 design. The model-based dose-escalation decisions to help inform the final decision by the SMC can be precalculated under the mTPI design and are presented in a 2-way table ([Table 4-2](#)).

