**Table 4-1: Study modules for dose escalation and expansion**

Module	Module description
Part A	Dose-escalation to identify the RP2D-M, based on emerging safety, PK, PD, and antitumor effect data. Participants will receive UCB6114 Q2W via iv infusion. The starting dose will be escalated (or de-escalated) stepwise in successive cohorts of 3 to 6 evaluable participants (modified rolling-6 design) (see Section 4.1.2), until the RP2D-M is determined. Up to 42 participants may be enrolled.
Part A1	Dose-optimization to evaluate alternative dosing schedules for UCB6114 administered as monotherapy in participant with unresectable locally advanced or metastatic colorectal adenocarcinoma, gastric adenocarcinoma, adenocarcinoma of the gastroesophageal junction, or pancreatic cancer. Based on emerging data from Part A, this module will evaluate a new dose formulation, different frequencies of dosing (eg, Q3W, QW4), and different time of infusion. Up to 32 participants may be enrolled.
Part B	Dose-escalation with TFD/TPI in participants with unresectable locally advanced or metastatic colorectal adenocarcinoma, gastric adenocarcinoma, or adenocarcinoma of the gastroesophageal junction to identify the RP2D-T.  The starting dose of UCB6114 in Part B will depend on the dose level evaluated in Cohort 3 of Part A (anticipated to be 500mg Q2W iv) and the emerging safety profile of UCB6114 monotherapy, including any overlapping toxicity with TFD/TPI. It is expected that 2 or 3 dose levels of UCB6114 will be explored. The starting dose will be escalated stepwise in successive cohorts of 2 to 4 evaluable participants (mTPI design), until the RP2D-T is determined. Up to 27 participants may be enrolled.

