**Table 4-2: Part B dose escalation/de-escalation schema for mTPI designa**

Number of DLTs	Number of participants treated at dose level						
	3	4	5	6	7	8	9
0	E	E	E	E	E	E	E
1	S	S	S	S	E	E	E
2	D	D	S	S	S	S	S
3	DR	DR	DR	D	S	S	S
4		DR	DR	DR	DR	DR	D
5			DR	DR	DR	DR	DR
6				DR	DR	DR	DR

D=de-escalate to next lower dose; DLT=dose-limiting toxicity; DR=the current dose is unacceptably toxic; E=escalate to next higher dose; mTPI= modified toxicity probability interval; S=stay at current dose

a Target toxicity=0.25

**Table 4-2** has the following interpretation (using 3 and 6 treated participants as examples):

With 3 participants treated at current dose level:

- 0 DLTs = escalate
- 1 DLT = remain at the current dose
- 2 DLTs = de-escalate
- 3 DLTs = de-escalate and consider current dose as unacceptably toxic

With 6 participants treated at current dose level:

- 0 DLTs = escalate
- 1 to 2 DLTs = remain at the current dose
- 3 DLTs = de-escalate
- >3 DLTs = de-escalate and consider current dose as unacceptably toxic

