## DLT Evaluatable Set

The DLT Evaluatable Set (DES) will include all study participants who, during the DLT assessment period:

- Receive the planned dose of UCB6114 (Part A and Part A1)
- Receive the planned dose of UCB6114 and at least 80% of the planned dose of TFD/TPI (Part B)
- Receive the planned dose of UCB6114 and at least 80% of the planned dose of mFOLFOX6 (Part C)
- Stopped treatment because of a DLT (any part of the study)

The DES will be used by the SMC for all dose escalation/de-escalation decision making.

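### The mTPI rule and Tables 4-2 and 4-3 count participants treated, while Section 10.1 bases every escalation decision on the DLT-evaluable set

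*Protocol*

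**What the plan says.** Sections 4.1.4.2.2 (Part B) and 4.1.5.2.2 (Part C) give the same account of the mTPI calculation: it is "calculated using data from all participants treated in prior and current cohorts at the same dose level". The column heading of Tables 4-2 and 4-3 is "Number of participants treated at dose level", and the worked examples under both tables also speak of 3 or 6 participants treated.

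Section 10.1 defines the DES and then states: "The DES will be used by the SMC for all dose escalation/de-escalation decision making". To be in the DES in Part B, a participant needs the planned UCB6114 and at least 80% of the planned TFD/TPI during the DLT period. Part C has the same rule with mFOLFOX6. The only other way in is to have stopped treatment because of a DLT.

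Other places lean towards evaluable participants. Table 4-1 sizes the mTPI cohorts in evaluable participants. Section 4.1.4 says "Each dose level may have more than one cohort and will have a minimum of 3 evaluable participants", and Section 4.1.5 repeats this. Section 10.6 treats anyone who leaves the study before all Cycle 1 UCB6114 doses as nonevaluable and to be replaced, unless a DLT came first. No passage says that the tables' column counts DES participants.

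**The concern.** The number at the top of the column decides which cell applies. A participant who received some treatment, fell short of the DES dosing rule and had no DLT is in the count under Section 4 and out of it under Section 10.1. Such a participant adds to the denominator and nothing to the numerator, although the planned exposure was not received. The apparent DLT rate falls, and the table can point to a different decision.

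The situation is realistic. TFD/TPI is taken twice daily on 10 days of Cycle 1, so 20 doses are planned. Missing five leaves 15/20 = 75%, below the 80% threshold, and Section 4.3.3.2.1 does not allow missed or vomited doses to be retaken. The tables inform the MTD of each combination, and through it RP2D-T and RP2D-F.

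**Working it through.** **Inputs.** Target DLT rate 0.25 and equivalence interval 0.20 to 0.30 (Sections 4.1.4.2.2 and 4.1.5.2.2; table footnote "Target toxicity=0.25"). Printed decisions for 0 to 6 DLTs in 3 to 9 participants (Table 4-2; Table 4-3 is identical). Codes: E escalate, S stay, D de-escalate, DR current dose unacceptably toxic. The protocol states neither the prior nor the DR cutoff. I assumed a Beta(1,1) prior, and DR when Pr(p > 0.25) exceeds 0.95.

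**Step 1: reproduce the printed table.** With x DLTs in n participants the posterior is Beta(1+x, 1+n−x). The decision is the largest of:

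- E: Pr(p < 0.20)/0.20
- S: Pr(0.20 < p < 0.30)/0.10
- D: Pr(p > 0.30)/0.70

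The DR rule overrides these. All 43 filled cells reproduce. Of the six combinations tried (priors Beta(1,1), Beta(0.5,0.5) and Beta(0.005,0.005), each with cutoffs 0.95 and 0.90), only Beta(1,1) with 0.95 matches every cell. The table is therefore correct for whatever n is put into it. Only the label on n is in doubt.

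**Step 2: add one nonevaluable, DLT-free participant.** Keep x and move from n to n+1. There are 36 such adjacent pairs, and 5 change:

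| DLTs | Evaluable only | One more counted | Effect |
|---|---|---|---|
| 1 | 1/6: S | 1/7: E | next dose higher |
| 2 | 2/4: D | 2/5: S | next dose higher |
| 3 | 3/6: D | 3/7: S | next dose higher |
| 3 | 3/5: DR | 3/6: D | still de-escalates, toxicity label lost |
| 4 | 4/8: DR | 4/9: D | still de-escalates, toxicity label lost |

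These can be read straight from the printed table and do not depend on the assumed prior or cutoff.

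**Step 3: the values behind the changes (E, S, D in order).**

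- 1/6: 2.116, 2.473, 0.471, so S. 1/7: 2.483, 2.480, 0.365, so E by a narrow margin.
- 2/4: 0.290, 1.052, 1.196, so D. 2/5: 0.494, 1.568, 1.063, so S.
- 3/6: 0.167, 0.927, 1.249, so D. 3/7: 0.281, 1.378, 1.151, so S.
- 3/5 to 3/6: Pr(p > 0.25) falls from 0.962 to 0.929, below the 0.95 cutoff.
- 4/8 to 4/9: it falls from 0.951 to 0.922.

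**Step 4: two such participants.** Of 29 comparisons from n to n+2, 8 change. The largest is 3/5 DR to 3/7 S.

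**Step 5: the reverse case.** Suppose a participant has a DLT, interrupts TFD/TPI, ends below 80% and later resumes. On a literal reading this person neither met the dosing rule nor stopped because of a DLT, so may fall outside the DES. With three other evaluable participants, one of whom had a DLT, the DES reads 1/3: S. The treated count reads 2/4: D. Here the treated count is the more cautious one.

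**The case against.** The strongest reply is that the intent is already plain. Section 10.1 is explicit. Table 4-1 and Sections 4.1.4 and 4.1.5 speak of evaluable participants, and so do the RP2D definitions in 4.1.4.3 and 4.1.5.3. Section 10.6 rules early dropouts nonevaluable and replaces them. The sentence in 4.1.4.2.2 can be read as saying only that cohorts at one dose level are pooled. The table informs the committee and does not bind it, all available safety data are considered, and neither RP2D-T nor RP2D-F may exceed RP2D-M.

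Most of this stands and limits the consequence. It does not remove the contradiction. No order of precedence is stated, and the decision table carries the other label. Replacing a participant does not help on the literal reading, because the replaced person was still treated. The Section 10.6 dropout rule concerns UCB6114 doses and leaving the study. It does not cover someone who stays on study but received less than 80% of the chemotherapy.

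Three stronger readings are tempting and are not supported:

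- A reader might infer that counting treated participants always errs towards the higher dose. Step 5 shows that it need not, and 31 of the 36 one-step comparisons do not change at all.
- A reader might infer that 0 DLTs in 3 treated, with only 2 evaluable, would permit escalation. The minimum of 3 evaluable participants in 4.1.4 and 4.1.5 blocks that.
- A reader might see a conflict between the minimum of 3 evaluable in those sections and 3 participants in 4.1.4.2.2 and 4.1.5.2.2. Three evaluable participants satisfy both.

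**Conclusion.** The point holds as a contradiction in the decision denominator, alike in Parts B and C. The probable intent is the DES, so this is a wording fault in an operative rule and not a flaw in the mTPI design or its table. For one nonevaluable, DLT-free participant, 5 of 36 comparisons move in the less cautious direction: three raise the indicated dose for the next cohort and two drop only the toxicity label. That direction depends on the extra participant being free of DLTs. The protocol gives no expected frequency of nonevaluable participants, so I cannot say how often a decision would be affected. It is worth correcting because the committee should not be able to reach two different cells of one table from two sections of one protocol.

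**What to change.** - In 4.1.4.2.2, 4.1.5.2.2 and Tables 4-2 and 4-3, replace the treated wording with DLT-evaluable participants as defined in Section 10.1, in the text, column headings and worked examples.
- Apply the minimum of 3, and the stopping criterion of 9 participants at the predicted MTD, to that set.
- Reword the DES so that any treated participant with a DLT in the window counts, whether or not treatment was stopped. This fits Section 10.6, which keeps participants who had a DLT before withdrawing. Without it, a plain switch to the DES could drop real DLTs from the numerator.
- State whether the maximum of 9 per dose level and the cap of 27 count treated or evaluable participants. Three levels of 9 use all 27 (3 × 9 = 27), so if both limits counted evaluable participants, a single replacement would bring the number treated to 28.

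The cost is an amendment to wording, with no new analysis. A decision may wait for a replacement participant, which Section 10.6 already allows. The one real choice for the sponsor is how the caps are counted, since that can affect enrollment.

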**Table 4-2: Part B dose escalation/de-escalation schema for mTPI designa**

Number of DLTs	Number of participants treated at dose level						
	3	4	5	6	7	8	9
0	E	E	E	E	E	E	E
1	S	S	S	S	E	E	E
2	D	D	S	S	S	S	S
3	DR	DR	DR	D	S	S	S
4		DR	DR	DR	DR	DR	D
5			DR	DR	DR	DR	DR
6				DR	DR	DR	DR

D=de-escalate to next lower dose; DLT=dose-limiting toxicity; DR=the current dose is unacceptably toxic; E=escalate to next higher dose; mTPI= modified toxicity probability interval; S=stay at current dose

a Target toxicity=0.25

**Table 4-2** has the following interpretation (using 3 and 6 treated participants as examples):

With 3 participants treated at current dose level:

- 0 DLTs = escalate
- 1 DLT = remain at the current dose
- 2 DLTs = de-escalate
- 3 DLTs = de-escalate and consider current dose as unacceptably toxic

With 6 participants treated at current dose level:

- 0 DLTs = escalate
- 1 to 2 DLTs = remain at the current dose
- 3 DLTs = de-escalate
- >3 DLTs = de-escalate and consider current dose as unacceptably toxic

#### **4.1.4.3 Definition of recommended Phase 2 dose in combination with TFD/TPI**

The RP2D-T will be defined after all participants evaluable for DLT assessment in Part B have completed a minimum of 28 days of treatment (ie, 1 cycle). The RP2D-T will not exceed the RP2D-M or the MTD (if an MTD is established). The definition of the RP2D-T will take into account the safety profile, PK, PD biomarkers, and any antitumor effect data.

#### **4.1.5 Part C – Dose escalation with mFOLFOX6**

Part C is a single arm, open-label, multiple ascending dose-escalation module of ONC001 evaluating UCB6114 in combination with a mFOLFOX6 to identify the recommended Phase 2 dose of UCB6114 when used in combination with mFOLFOX6 (RP2D-F). Up to 27 participants

with unresectable locally advanced or metastatic colorectal adenocarcinoma, gastric adenocarcinoma, and adenocarcinoma of the gastroesophageal junction will be enrolled.

Part C of ONC001 is planned to be initiated after Cohort 3 of Part A has completed the 28-day DLT assessment period and once the SMC has provided a recommendation to dose escalate to the next protocol-defined level in Part A of the study. Eligible participants will receive UCB6114 as an iv infusion Q2W in combination with iv mFOLFOX6 (Q2W) on a 28-day cycle. A mFOLFOX6 regimen will be administered at the recommended standard of care dose: oxaliplatin 85mg/m^2 iv infusion on Day 1, leucovorin 400mg/m^2 iv infusion on Day 1, 5-fluorouracil 400mg/m^2 iv bolus on Day 1, followed by 5-fluorouracil 1200mg/m^2/day continuous infusion on Day 1 and Day 2 (2400mg/m^2 over 46 hours). The starting dose of UCB6114 in Part C will depend on the dose level evaluated in Cohort 3 of Part A (anticipated to be 500mg Q2W iv), and the emerging safety profile of UCB6114 monotherapy, including any overlapping toxicity with the mFOLFOX6 regimen.

Part C will be undertaken using the mTPI method. A target DLT rate of 25% with an equivalence interval (20% to 30%) will be used to estimate MTD during dose escalation. For all dose levels, enrolled participants will be treated in cohorts of 2 to 4 participants (target of 3), who can be treated in parallel. Each dose level may have more than one cohort and will have a minimum of 3 evaluable participants.

It is expected that up to 3 dose levels of UCB6114 will be explored in combination with the selected mFOLFOX6 dosing regimen. However, additional dose levels may be added based on emerging data and recommendations of the SMC. Dose escalation steps are currently planned at a maximum of 2-fold. Escalating dose levels in Part C will not exceed a dose level tested and considered safe by the SMC to allow dose escalation in monotherapy (Part A).

The decision to dose escalate, have no change in dose, or dose de-escalate in the next cohort will occur once all participants in the preceding cohort have been monitored for a minimum of 28 days (ie, 1 cycle). All available safety data (both within the cohort and from preceding cohorts and other parts of the study) will be taken into consideration when dose escalation decisions are made. The dose justification is given below in Section 4.3.3.

The planned duration of treatment is 2 cycles. Participants may, however, remain in the study for additional cycles if they are receiving a therapeutic benefit (SD, PR, or CR) or until they fulfill one of the criteria for study discontinuation (Section 4.3.3). Participants will continue treatment until disease progression, unmanageable toxicity, or withdrawal of consent. Upon discontinuation from treatment, participants will be referred to appropriate follow-up care per the investigator's judgment.

From Part C, a RP2D-F for UCB6114 in combination with mFOLFOX6 will be determined based upon the totality of information, including the safety profile, PK data, PD biomarker data, and available antitumor activity.

